7.2.15 Quality of Life Assessment

Quality of life will be assessed by validated EORTC QLQ-C30 questionnaire. As a self-administered survey, it incorporates 30 items comprising five functional scales (physical, role, cognitive, emotional,

and social), three symptom scales (fatigue, pain, and nausea and vomiting), as well as a global health and QoL scale. It will be completed by the patient at the time points listed below:

- Within 7 days prior to start of study treatment
- Prior to dose administration on Day 1 of Cycles ≥ 2
- At the 30-day safety follow-up (if not performed within the prior 4 weeks)

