7.2.17 End of Treatment

The end of treatment is defined as the date when the Investigator determines that the patient will stop all study medication. If the decision to discontinue study medication is made within 2 weeks after the patient's last treatment visit, an End of Treatment Visit is not required unless deemed clinically necessary by the Investigator. If the decision to discontinue study medication (due to disease progression or other reasons) is made more than 2 weeks after the last treatment visit, an End of Treatment Visit is required. If this visit occurs within 2 weeks of the 30-day Safety Follow-up Visit, the 2 visits can be combined.

7.2.18 30-Day Safety Follow-up

A Safety Follow-up visit will be conducted 30 days after the last dose of study medication. If the patient starts new anticancer therapy within 30 days after the last dose of study medication, the 30-day Safety Follow-up Visit should be performed prior to the start of new anticancer therapy within the 30-day window. If this visit occurs within 2 weeks of the End of Treatment Visit, the 2 visits can be combined but should not take place less than 30 days after the last dose of study medication.

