7.3 Outcome Measures

7.3.1 Primary Outcome:

- **16-week progression-free survival (PFS) rate:** The percentage of study population alive and without progression (according to RECIST 1.1) at 16 weeks from the date of informed consent

7.3.2 Secondary Outcomes:

- **Progression-free Survival (PFS):** PFS is measured from the date of informed consent to radiographically documented progression according to RECIST 1.1 or death from any cause (whichever occurs first). Participants alive and without disease progression or lost to follow-up will be censored at the date of their last radiographic assessment
- **Time to progression (TTP):** TTP is measured from the date of informed consent to radiographically documented progression according to RECIST 1.1. Participants death and without disease progression, alive without disease progression, or lost to follow-up will be censored at the date of their last radiographic assessment
- **Overall survival (OS):** OS is measured from date of informed consent to the date of death from any cause. Participants alive or lost to follow-up will be censored at the date of their last radiographic assessment
- **Objective response rate (ORR):** The percentage of patients with radiologically complete or partial response as determined by the Investigator according to RECIST version 1.1.
- **Disease control rate (DCR):** The percentage of patients with radiologically complete response, partial response, or stable disease as determined by the Investigators according to RECIST version 1.1
- **Duration of response (DoR):** DoR is the time from documentation of tumor response to radiographically documented disease progression
- **Time to deterioration of ECOG performance status:** Time from date of informed consent until the first date on which ECOG performance status score of 2 or higher was recorded ⁽³⁶⁻³⁷⁾
- **Time to deterioration of quality of life:** Decrease from baseline of 10 points or more on the EORTC QLQ-C30 maintained for two consecutive assessments or a decrease of 10 points or more in one assessment followed by death from any cause within 3 weeks.
- **Safety outcome measures:** Incidence, nature, and severity of adverse events graded according to NCI-CTCAE v5.0

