(5) Quality of Life: Patients should complete the EORTC QLQ-C30 questionnaires within 7 days prior to start of study treatment, prior to dose administration on Day 1 of Cycles ≥ 2 , and at the 30-day safety follow-up if not performed within the prior 4 weeks.

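### A QLQ-C30 drop first seen on the last collected form cannot count as deterioration unless death follows within 3 weeks, because no later form is scheduled to confirm it

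*Protocol*

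**What the plan says.** Section 2.2 lists time to deterioration of quality of life as the eighth secondary objective. Section 7.3.2 gives two routes to an event. The first is "Decrease from baseline of 10 points or more on the EORTC QLQ-C30 maintained for two consecutive assessments". The second is "a decrease of 10 points or more in one assessment followed by death from any cause within 3 weeks". No censoring rule is given for this endpoint.

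Section 7.2.15 sets the collection times: within 7 days before treatment starts, then "Prior to dose administration on Day 1 of Cycles" 2 and later, then "At the 30-day safety follow-up (if not performed within the prior 4 weeks"). Appendix 1, footnote 5, repeats this schedule: "prior to dose administration on Day 1 of Cycles ≥ 2 , and at the 30-day safety follow-up if not performed within the prior 4 weeks". Neither place lists a form at the End of Treatment visit. After the 30-day visit the protocol continues survival status (7.2.19) and, where progression has not yet been seen, tumour imaging (7.2.12), but no questionnaire.

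On the timing of that last visit, 7.2.18 says "A Safety Follow-up visit will be conducted 30 days after the last dose of study medication". For a patient starting another treatment sooner, "the 30-day Safety Follow-up Visit should be performed prior to the start of new anticancer therapy within the 30-day window".

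**The concern.** A rule that needs confirmation works only if a further form follows the first drop. Here collection stops at about the time patients leave treatment, and the 4-week waiver can remove the final form even though the visit takes place. RECIST and clinical progression are the first two removal criteria in 7.4, so deterioration that accompanies progression is likely to appear late in the form sequence, where confirmation is hardest.

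If such drops are not events, they are missing for a reason tied to the outcome, and time to deterioration on TAS-102 would tend to look longer than it is. The performance-status endpoint does not share the problem: ECOG is recorded at both End of Treatment and the 30-day visit (7.2.8), and 7.3.2 requires only one score of 2 or higher.

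**Working it through.** The protocol states no figure on this point to reproduce, so the check is visit-date arithmetic followed by an illustration.

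**Inputs.** Cycles last 28 days, and a full cycle's last dose is on Day 12 (6.3.1). Scans are every 8 weeks from the start of treatment (7.2.12), that is, every two cycles. Scans and follow-up visits have a window of ±7 days (7.1). The safety visit is 30 days after the last dose (7.2.18). The waiver limit is 4 weeks, or 28 days (7.2.15).

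**Patient stopped at the week-8 scan before Cycle 3 is dosed.** Day 1 is Cycle 1 Day 1.
- Cycle 2 Day 1: 28 + 1 = day 29, form completed.
- Last dose, Cycle 2 Day 12: 29 + 11 = day 40.
- Planned Cycle 3 Day 1: 56 + 1 = day 57.
- 30-day visit: 40 + 30 = day 70.

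| Case | Forms after day 29 | Can a drop starting after day 29 be confirmed? |
|---|---|---|
| Form completed on day 57, no dose given | Day 57 only; day 70 is waived because 70 − 57 = 13 days | No |
| No form on day 57, since no dose is given | Day 70 only | No |

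In both cases one form follows day 29, so a later drop counts only through the death route. The same gaps arise at week 16: Cycle 4 Day 1 is day 85, the last dose day 96, the next Day 1 day 113 and the safety visit day 126.

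**When confirmation does work.** If no Day 1 form follows the last dosed cycle, the gap from that cycle's Day 1 form to the safety visit is (cycle day of last dose − 1) + 30.
- Last dose on Day 12: 11 + 30 = 41 days (34 to 48 with the window).
- Last dose on Day 8, 5 or 1: 37, 34 or 30 days.

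All these nominal gaps exceed 28 days, so the final form is due, and a drop already present on Day 1 of the last dosed cycle can be confirmed. The waiver would apply only to a visit early in its window (for example 30 − 7 = 23 days, or 34 − 7 = 27 days) or one brought forward for new therapy.

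A late scan also helps. With the scan on day 63 and Cycle 3 begun, the form is on day 57, the last dose on day 61 and the safety visit on day 91. The gap is 34 days, so the second form is due.

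**Illustrative size.** Assume that a lasting drop begins at tumour progression, that progression is exponential, and that every stop occurs at the 8-weekly scan before the next dose. A drop that starts in the second 4 weeks of a scan interval is then seen on one form only. With h = ln 2 / median (in weeks) and q = exp(−4h), the share of drops in the second half of an interval is (q − q²)/(1 − q²) = q/(1 + q).

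| Median PFS | Weeks (× 4.348) | q | Share seen once |
|---|---|---|---|
| 1.6 months (lowest in Tables 1 and 2) | 6.96 | 0.671 | 0.40 |
| 2.5 months (intermediate value, assumed) | 10.87 | 0.775 | 0.44 |
| 4.1 months (highest in Tables 1 and 2) | 17.83 | 0.856 | 0.46 |

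Under the same model, 1 − exp(−8h) gives 55% (median 1.6 months) to 27% (4.1 months) of patients progressing by week 8. Stopped before Cycle 3 dosing, they would have at most two post-baseline forms, both of which must show the drop.

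**The case against.** A reader might infer that a drop around progression can almost never count. The documents do not support that. The illustration itself leaves 54% to 60% of such drops confirmable, the death route adds some of the rest, and a scan after the next cycle has started restores a second form.

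A reader might also take the 4-week waiver as the general cause. It is not. After a dosed cycle the nominal gap is 30 to 41 days and the form is due. The waiver acts mainly when a Day 1 form is completed but no dose follows, or when the visit is early or brought forward. Because Day 1 forms are tied to dosing, it is not even clear that a form is due when no dose is given.

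The size is conditional too. Nothing in the protocol shows that quality of life falls at the moment of progression. Patients may stop for toxicity or clinical progression away from a scan, and drops that start earlier would lower the uncounted share. Deaths within 3 weeks are not quantified. How an unconfirmed last drop is censored is not stated, and 9.2 refers missing-data handling for secondary efficacy analyses to the SAP. Requiring confirmation is also a legitimate guard against transient drops, and the definition and schedule do not contradict each other.

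These points narrow the concern without removing it. Both the event definition and the schedule are fixed in the protocol, and a SAP cannot recover a form that was never collected.

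**Conclusion.** The point holds in this limited form: a drop of 10 points or more first seen on the last collected form is not an event under 7.3.2 unless death follows within 3 weeks. For a patient stopped at a scan before the next cycle is dosed, this covers every drop starting after Day 1 of the last dosed cycle. That part is date arithmetic and needs no distributional assumption.

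The 40% to 46% is an illustration that rests on the three assumptions given with it, before subtracting early deaths; it is not an estimate for this trial. Overstatement of time to deterioration is the likely direction, but a reader who concludes that these patients will be recorded as not deteriorated goes beyond the text. Only a secondary endpoint is affected; the decision rule in 9.3 uses 16-week PFS alone. The change is worth making because it is cheap.

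**What to change.** 1. In 7.2.15 and Appendix 1, footnote 5, delete the condition that waives the 30-day form when one was completed in the prior 4 weeks. In the worked example, a drop on the day-57 form could then be confirmed on day 70. This does not help when the 30-day form is the first to show the drop.
2. For that remaining case, add to 7.3.2 that a decrease of 10 points or more on the last available form, with no later form, counts as an event on that form's date, at least as a stated sensitivity analysis. This extends the approach of the existing death route, which already accepts one unconfirmed drop.

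The cost is a protocol amendment and, for some patients, one extra self-completed form at a visit that already takes place. The downside is that some transient drops on the last form will count as events; reporting results with and without the second rule would show how much that matters.

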7.4 Criteria for Removal from Protocol Treatment

- RECIST-defined disease progression
- Clinical progression
- Patient experiences an irreversible, treatment-related, Grade 4, clinically relevant, non-hematologic event.
- Inter-current disease that would affect assessments of clinical status to a significant degree, require discontinuation of drug, or both.
- Unacceptable adverse events, or change in underlying condition such that the patient can no longer tolerate therapy, including:
 - (a) A maximum dose delay >28 days from the scheduled start date of the next cycle.
 - (b) Need for more than 3 dose reductions of study medication
- Physician's decision including need for other anticancer therapy not specified in the protocol or surgery or radiotherapy to the only site(s) of disease being evaluated in this protocol
- Patient's request irrespective of the reason

8 SAFETY REPORTING

8.1 Adverse Events (AEs)

- According to the ICH guideline for Good Clinical Practice, an adverse event is any untoward medical occurrence in a clinical investigation subject administered a pharmaceutical product, regardless of causal attribution. An adverse event can therefore be any of the following:
- Any unfavorable and unintended sign (including an abnormal laboratory finding), symptom, or disease temporally associated with the use of a medicinal product, whether or not considered related to the medicinal product
- Any new disease or exacerbation of an existing disease (a worsening in the character, frequency, or severity of a known condition)
- Recurrence of an intermittent medical condition (e.g., headache) not present at baseline
- Any deterioration in a laboratory value or other clinical test (e.g., ECG, X-ray) that is associated with symptoms or leads to a change in study treatment or concomitant treatment or discontinuation from study drug
- Adverse events that are related to a protocol-mandated intervention, including those that occur prior to assignment of study treatment (e.g., screening invasive procedures such as biopsies)

8.2 Serious Adverse Events (SAEs)

- A serious adverse event is any adverse event that meets any of the following criteria:
 - Is fatal (i.e., the adverse event actually causes or leads to death)
 - Is life threatening (i.e., the adverse event, in the view of the Investigator(s), places the patient at immediate risk of death)
 - This does not include any adverse event that, had it occurred in a more severe form or was allowed to continue, might have caused death.
 - Requires or prolongs inpatient hospitalization
 - Results in persistent or significant disability/incapacity (i.e., the adverse event results in substantial disruption of the patient's ability to conduct normal life functions)
 - Is a congenital anomaly/birth defect in a neonate/infant born to a mother exposed to study drug
 - Is a significant medical event in the Investigator(s)'s judgment (e.g., may jeopardize the patient or may require medical/surgical intervention to prevent one of the outcomes listed above)
- The terms “severe” and “serious” are not synonymous. Severity refers to the intensity of an adverse event (e.g., rated as mild, moderate, or severe, or according to National Cancer Institute Common Terminology Criteria for Adverse Events [NCI-CTCAE]; the event itself may be of relatively minor medical significance (such as severe headache without any further findings).
- Severity and seriousness need to be independently assessed for each adverse event recorded in the clinical database.

8.3 Pregnancy Reports

- Female patients of childbearing potential will be instructed to immediately inform the Investigator(s) if they become pregnant during the study.

8.4 Assessment of Causality of Adverse Events

Investigator(s) should use their knowledge of the patient, the circumstances surrounding the event, and an evaluation of any potential alternative causes to determine whether an adverse event is considered to be related to the study drug, indicating “Yes” or “No” accordingly. The following guidance should be taken into consideration:

- Temporal relationship of event onset to the initiation of study drug
- Course of the event, with special consideration of the effects of dose reduction,
- Discontinuation of study drug, or reintroduction of study drug (as applicable)
- Known association of the event with the study drug or with similar treatments
- Known association of the event with the disease under study
- Presence of risk factors in the patient or use of concomitant medications known to increase the occurrence of the event
- Presence of non-treatment-related factors that are known to be associated with the occurrence of the event

8.5 Methods of Recording Adverse Events

- All AEs must be documented in the appropriate section of the CRF. An SAE report form (initial or follow up) must be completed in case of any of the seriousness criteria is met.
- The following aspects must be recorded for each event in the CRF:
 - A description of the AE in medical terms, not as reported by the subject;
 - The date of onset (start date)
 - The time of onset (start time)
 - The date of recovery (stop date)
 - The time of recovery (stop time)
 - The severity of the sign and/or symptom or clinically significant abnormal laboratory value according to NCI-CTCAE v.5. If no toxicity grade is described for a given sign, symptom or abnormal laboratory value, the Investigator(s) will grade the severity as mid (grade 1), moderate (grade 2), severe (grade 3), or life-threatening or disabling (grade 4).
 - Death (grade 5) as defined by NCI-CTCAE v.5 is mainly regarded as an outcome and will be documented accordingly (see below).
- The causal relationship to TAS-102 as assessed by the Investigator(s); the decisive factor in the documentation is the temporal relation between the AE and the study drug. The following judgments of the causality to study drug or study procedures are to be used:
 - Not Related = not suspected to be reasonably related to the investigational product. AE could not medically (pharmacologically/ clinically) be attributed to the investigational product under study in this protocol
 - Related = suspected to be reasonably related to the investigational product. AE could

- medically (pharmacologically/ clinically) be attributed to the investigational product under study in this protocol
- Action taken on TAS-102 (none, medication discontinued, dose reduction, medication delayed, reduction of infusion rate).
- Other action (none, concomitant medication given, new or prolonged hospitalization, procedural surgery).
- The outcome according to the following definitions:
 - Recovered without sequelae (AE disappeared)
 - Recovered with sequelae (AE has resulted in permanent disability/incapacity)
 - Not yet recovered
 - Not recovered at death
 - Change in toxicity grade/severity or seriousness (e.g., an AE with no change of toxicity grade but newly classified as an SAE due to hospitalization)
 - Fatal (AE resulted in death)
- Concomitant medication given: Yes or No (Note: If this question is answered “Yes” the corresponding serious criteria must be ticked)
 - Subject died
 - Life-threatening
 - New or prolonged hospitalization
 - Persistent/significant disability
 - Congenital abnormality
 - Important medical event
 - Seriousness: Yes or No
- If in any one patient the same AE occurs on several occasions, then the AE in question must be documented and assessed anew each time.

8.6 Procedure of Reporting Serious Adverse Events

- The Sponsor-Investigator(s) primary responsibilities for safety reporting are to identify and follow-up on Serious Adverse Events (SAEs) experienced by participants in the study and to forward the information to the local regulatory authorities and Taiho, as required by local regulations (for regulatory reporting) and as required by the Investigator Sponsored Study (ISS) agreement (for reporting to Taiho).
- The following reportable events must be submitted to Taiho within 2 business days or 3 calendar days (whichever comes first) using the applicable safety report form provided. The Principal Investigator(s) will assume responsibility for submitting the reportable event(s) to Taiho as well as ensuring that any local reporting requirements are completed in parallel.
- Serious Adverse Events (see section 6.4.2)
 - Exposure during Pregnancy or Breastfeeding (even not associated with adverse event)
 - Occupational exposure (even not associated with adverse event)

8.7 Monitoring of subjects with Adverse Events

- Any AE that occurs in the course of a clinical study must be monitored and followed up until the last study visit. It is the responsibility of the Investigator(s) that any necessary additional therapeutic measures and follow-up procedures are performed.

9 STATISTICS

9.1 Statistical Analysis

16-week PFS rate will be estimated by Kaplan-Meier method and expressed based on exact binomial distribution. Other survival outcomes including TTP, PFS, OS and their corresponding 95% confidence interval will be estimated using Kaplan-Meier method.

All of the reported P values will be 2-tailed, and $P < 0.05$ will be considered statistically significant. No multiplicity will be considered. The analyses will be performed using statistical software packages SPSS and R.

9.2 Procedures for Handling Missing, Unused, and Spurious Data

All available data will be included in the data listings and tabulations. Where appropriate, imputations of values for missing data for primary and secondary efficacy analyses will be performed as specified in the Statistical Analysis Plan. All data recorded on the CRF will be included in the data listings that will accompany the clinical study report.

If, after the study has begun, but prior to the conduct of any analysis, changes made to primary and / or key secondary endpoints, or the statistical methods related to those hypotheses, then the protocol will be amended. Changes to exploratory analyses made after the protocol finalized will be documented and referenced in the final report. Post hoc exploratory analyses will also be identified in the final report.

9.3 Sample Size Calculation

H0: The null hypothesis is that the 16-week PFS rate of 10% is similar to historical results.

H1: The alternative hypothesis of treatment efficacy: experimental treatment with TAS-102 would result in 16-week PFS rate of 30%.

To detect 20% of differences from 10% to 30% in the 16-week PFS rate, with Type I error of 0.05 and 80% power, and assuming 10% drop out rate, the target sample size is 28 patients.

The null hypothesis will be rejected if 6 or more out of first 25 evaluable patients are progression-free and alive at 16 weeks, the treatment will be considered worthy of further investigation. Otherwise, if 5 or fewer patients were progression-free and alive at 16 weeks in the 25 evaluable patients, this regimen would have been considered ineffective in this patient population.

Patients may drop out before their 16-week PFS rate can be assessed. Such patients will be excluded for the primary endpoint assessment and will be replaced by other patients that 16-week PFS rate can be assessed. We assume 50% of screened population will be eligible for the study, thus we plan to screen for 56 patients.

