1 BACKGROUND

1.1 Background of the Study Population

Pancreatic ductal adenocarcinoma (PDA) is a lethal cancer with 5-year survival rate < 5%. ⁽¹⁾ Majority of patients presented late when curative resection is impossible. For patients with locally advanced or metastatic disease, gemcitabine-based therapies have been the standard of care for the past two decades. ⁽²⁾ Until recently, two combination regimes, namely FOLFIRINOX (a combination of oxaliplatin, folinic acid, and 5-fluorouracil, 5-FU) and albumin-bound paclitaxel in combination with gemcitabine, have demonstrated their survival advantages over gemcitabine mono-therapy and accepted as front-line treatments. ⁽³⁻⁴⁾ Despite these advances, progression is inevitable; there are limited options and no universally accepted standard among patients who progressed after front-line treatment. There is a huge unmet need in this population.

The use of subsequent lines of treatment has been increased over the past decade. Various second-line therapies have been studied and associated with improved survival in patients who have experienced progression on gemcitabine-based regimes. Primarily, fluoropyrimidine (FP) based regime is commonly studied in this setting. In NAPOLI-1, a large randomized phase 3 trial; the combination of 5-FU and nanoliposomal irinotecan (nal-IRI) demonstrated a significant survival advantage compared with 5-FU monotherapy (median overall survival of 6.1 months vs. 4.2 months, hazard ratio 0.67). Based on these results, the US Food and Drug Administration had approved this regime in patients with refractory pancreatic cancer. ⁽⁵⁾ Similarly, the CONKO-003 trial showed improved survival in patients who received combined oxaliplatin, leucovorin (LV), and 5-FU (OFF) compared with those who received 5-FU/LV. ⁽⁶⁾ However, results from the PANCREOX study suggested a potential detriment from the addition of oxaliplatin to 5FU/LV. ⁽⁷⁾ Table 1 summarized the selected randomized studies in evaluating second-line combination chemotherapy in gemcitabine-refractory PDA. The median progression-free survival was ranged from 1.6-3.8 months and overall survival was ranged from 3.3-9.9 months. ⁽⁵⁻¹¹⁾

Study	N	Treatment	Median PFS (months)	Median OS
Loka et al. (8)	127	S-1 + Irinotecan vs. S-1	3.5 vs. 1.9 months	6.8 vs. 5.8 months
Ueno et al. (9)	140	SL vs. S-1	3.8 vs. 2.7 months	6.3 vs. 6.1 months
Gill et al. (7)	108	mFOLFOX6 vs. 5FU/LV	3.1 vs. 2.9 months	6.1 vs. 9.9 months

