Wang-Gillam et al. (5)	417	Nal-IRI + 5FU/LV vs. Nal-IRI vs. 5FU/LV	3.1 vs. 2.7 vs. 1.6 months	6.1 vs. 4.9 vs. 4.2 months
Ohkawa et al. (10)	268	S-1 + Oxaliplatin vs. S-1	3.0 vs. 2.8 months	7.4 vs. 6.9 months
Oettle et al. (6)	160	OFF vs. FF	2.9 vs. 2.0 months	5.9 vs. 3.3 months
Ge et al. (11)	92	SL vs. S-1	3.0 vs. 1.9 months	6.3 vs. 5.5 months

Abbreviations: SL, TS-1 and leucovorin; 5FU, 5-fluorouracil; LV, leucovorin; Nal-IRI, nano-liposomal irinotecan

Table 1. Selected randomized studies of combination chemotherapy in gemcitabine-refractory pancreatic cancer patients

However, as patient's performance status often rapidly declines when tumor is locally or systemically progressing, it can be difficult to administer second-line combination chemotherapy in some patients. Several small single-arm phase II studies have demonstrated modest activity and favorable toxicity profile of single-agent chemotherapy (Table 2); therefore mono-agent chemotherapy may constitute a feasible treatment option in this setting.

Study	N	Treatment	Median PFS (months)	Median OS
Hosein et al. (12)	19	Nab-paclitaxel	1.7 months	7.3 months
Ko et al. (13)	40	Nal-IRI	2.4 months	5.2 months
Sudo et al. (14)	21	S-1	4.1 months	6.3 months
Yi et al. (15)	33	Irinotecan	2.0 months	6.6 months
Morizane et al. (16)	40	S-1	2.0 months	4.5 months
Boeck et al. (17)	39	Capecitabine	NA	7.6 months
Boeck et al. (18)	52	Pemetrexed	NA	5 months
Androulakis et al. (19)	18	Oxaliplatin	NA	3.5 months

Abbreviations: Nal-IRI, nano-liposomal irinotecan

Table 2. Single-armed phase II clinical trials evaluating second-line single-agent chemotherapy in advanced pancreatic cancer

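### Section 9.3 presents the 10% null for 16-week PFS as the historical rate, but gives no source and the protocol's own tables do not establish it, so 6 of 25 supports only a rate above 10%

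*Protocol*

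**What the plan says.** Section 9.3 words the null as "The null hypothesis is that the 16-week PFS rate of 10% is similar to historical results" and the alternative as "The alternative hypothesis of treatment efficacy: experimental treatment with TAS-102 would result in 16-week PFS rate of 30" (per cent). With 25 evaluable patients, six or more alive and progression-free at 16 weeks reject the null, and then "the treatment will be considered worthy of further investigation". No reference or derivation accompanies the 10%.

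The historical PFS data are in section 1.1. The text on the randomised studies says "The median progression-free survival was ranged from 1.6-3.8 months". Table 2, headed "Single-armed phase II clinical trials evaluating second-line single-agent chemotherapy in advanced pancreatic cancer", extends the range to 4.1 months. Both tables give medians only. No 16-week or 4-month PFS rate appears anywhere in the protocol.

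**The concern.** The 10% is the benchmark for the trial's only decision rule. The null is tied to past results and the alternative is labelled treatment efficacy, so a reader will take rejection of the null to mean that TAS-102 did better than earlier second-line treatment. That reading needs 10% to be what earlier treatment achieved. If the true historical rate is nearer 20% or 30%, a drug no better than existing options could pass the rule and be reported as an advance. The worth-pursuing conclusion is ordinary for phase II. The difficulty is the historical description attached to the null.

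**Working it through.** **1. The plan's own figures.** With X ~ Binomial(25, p):
- P(X ≥ 6 | p = 0.10) = 0.033, the exact one-sided alpha.
- P(X ≥ 6 | p = 0.30) = 0.807, the power. With 24 patients and the same cut-off it is 0.771.
- 25 / 0.9 = 27.8, rounded up to 28.

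The sample size and cut-off reproduce.

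**2. Without a model.** 16 weeks = 112 / 30.4375 = 3.68 months. Two arms have longer medians: S-1 plus leucovorin in Table 1 (3.8 months) and one S-1 study of 21 patients in Table 2 (4.1 months). About half or more of those patients were progression-free at 16 weeks.

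**3. With an assumed curve shape.** The other 18 arms need a model. Assume Weibull PFS with median m and shape k: S = 0.5^((3.68/m)^k). Shape 1 is a constant hazard; larger shapes are rising hazards.

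Inputs, in months:
- All 20 arms. Table 1: 3.5, 1.9, 3.8, 2.7, 3.1, 2.9, 3.1, 2.7, 1.6, 3.0, 2.8, 2.9, 2.0, 3.0, 1.9. Table 2: 1.7, 2.4, 4.1, 2.0, 2.0.
- The 13 single-agent arms, the closest comparators to TAS-102 monotherapy. Table 1: 1.9, 2.7, 2.7, 2.8, 1.9, plus the three 5-FU/folinic-acid controls, 2.9 ("mFOLFOX6 vs. 5FU/LV"), 1.6 ("3.1 vs. 2.7 vs. 1.6 months") and 2.0 ("2.9 vs. 2.0 months"). Table 2: 1.7, 2.4, 4.1, 2.0, 2.0.

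| 16-week PFS | k = 1 | k = 1.5 | k = 2 |
|---|---|---|---|
| Median 1.6 | 20% | 9% | 3% |
| Median 2.0 (middle single-agent arm) | 28% | 18% | 10% |
| Median 2.4 | 35% | 27% | 20% |
| Median 4.1 | 54% | 55% | 57% |
| Mean, 20 arms | 37% | 31% | 26% |
| Mean, 13 single-agent arms | 33% | 25% | 19% |
| Single-agent arms below 10% | 0 | 1 | 7 |

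At constant hazard, 10% would need a median of 3.68 × ln 2 / ln 10 = 1.1 months, shorter than any listed. At shape 2 the seven arms below 10% are those with medians of 2.0 months or less. The 13 of 20 arms at 2.4 months or more stay at about 20% or higher at all three shapes.

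**4. What the cut-off supports.** 6/25 = 24%. The exact two-sided 95% interval is 9.4% to 45.1%, and the one-sided 95% lower bound is 11.0%. So exactly six successes put the rate above 10% one-sided only; the two-sided interval, which matches the two-tailed convention of section 9.1, still contains 10%. A rate of 20% is well inside: P(X ≥ 6 | p = 0.20) = 0.38.

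**5. Chance of passing with no improvement.** A drug equal to a 2.0-month arm meets 6 of 25 with probability 0.74, 0.28 or 0.03 at shapes 1, 1.5 and 2. The last is about the design's own alpha. This is a range driven by the assumed shape, not an estimate.

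**The case against.** The strongest reply is that medians do not fix a 16-week rate and that 10% can arise in several ways. A rising hazard does it: at a 2.0-month median the shape needed is ln(ln 10 / ln 2) / ln(3.68 / 2.0) = 1.97. Scan timing can do it with a constant hazard: if 32% remain progression-free over each 8-week interval, 0.32² = 10% remain after the week-16 scan, while the observed median sits near the first scan, at about 1.9 months. The scan intervals of the cited studies are not in the protocol, so 8 weeks is an assumption. A later-line population could also do worse, and section 3.1 sets no upper limit on prior lines.

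This stands for the arms at 2.0 months or less. A reader might infer that 10% demands a steeply rising hazard or a later-line population; scan timing shows that it does not. A reader might also infer that the tables disprove 10%; they do not. But none of these routes brings the arms at 2.4 months or more to 10% at shapes up to 2 or through 8-weekly scanning, and the protocol argues none of them. Moreover, this trial counts 16 weeks from consent (section 7.3.1) and scans from the start of treatment (section 7.2.12). If the 16-week point falls before the week-16 scan, the same scan model reads about 26% to 32%, not 10%.

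It is also fair to say that section 9.3 claims superiority to no named regimen, and that a low-activity null is normal in phase II. Both are true. A threshold chosen by design needs no historical source; a statement that it matches history does.

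Finally, if 10% is below past activity, should the cut-off rise? The documents give no 16-week historical rate to reset it against, so they do not show that the cut-off is wrong.

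**Conclusion.** The historical label on the 10% null is unsupported by the protocol's own data. Model-free, two of 20 arms contradict it. With Weibull shapes 1 to 2, the average historical rate is 26% to 37% over all arms and 19% to 33% over single agents. These averages rest on the assumed shapes, are not weighted by study size, and count the 5-FU/folinic-acid controls as single-agent. A rate near 10% remains possible for the shortest-median arms, so the finding is that 10% is not established, not that it is false.

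Two stronger readings should be resisted. The sample size and cut-off are arithmetically sound. And the chance of passing with no improvement cannot be put at 74%: it runs from 0.74 to 0.03 with the assumed shape. What holds regardless of shape is that exactly 6 of 25 supports a rate above 10%, one-sided, and does not exclude a historical rate of 20%.

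**What to change.** Keep n and the 6-of-25 cut-off. In section 9.3, strike the clause that likens 10% to past results and write:

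> H0: the 16-week PFS rate is 10% or less, a minimum-activity threshold. Rejecting H0 shows (one-sided) that the rate exceeds 10%; it does not show improvement over the regimens in Tables 1 and 2.

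A citation for 10% alone would not be enough: even a sound later-line source would leave the comparison with Tables 1 and 2 unsupported. The cost is two sentences of protocol wording and a less favourable stated claim. Sample size, cut-off and analysis do not change.
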